Viral spread (for both outcomes)	Total lockdown Partial lockdown (geographical, step-wise/graduated response) Curfew School closure Closure of shopping malls, gyms, churches, parks Remote work Restrictions to national/subnational mobility Prohibition of mass gatherings
Health systems response (for COVID-19 deaths outcome)	Interventions to increase testing capacity Interventions to increase the number of ICU/critical beds
Mitigation strategies (for both outcomes)	Direct social assistance (in-kind/cash) Cash transfer Withdrawal of pension funds

Comparator

In an interrupted time series analysis, the comparator is a counterfactual outcome defined as the projection of the pre-intervention trend to simulate what would have happened if the policy had not occurred (see Statistical Analysis Plan for definitions).

Outcomes

We will assess three primary outcomes. The first outcome will be the 7-day moving average of daily confirmed cases of COVID-19/SARS-CoV-2. The second outcome is the time-varying reproductive number between the current and previous period.¹⁹ The third outcome is the 7-day moving average of the daily number of deaths by COVID-19 in Latin American subnational regions. For the statistical modelling, these averages will be rounded to the nearest integer. We will consider a 7-day lag as the primary lag. Details on sensitivity analyses can be found in the Statistical Analysis Plan.

We define the outcomes following the official national sources definitions, as each country applies its criteria to define the occurrences and the deaths caused by COVID-19. It is important to note that those criteria are not always clearly stated, but all subnational units are under the same measure at each time.

Data sources

We will obtain COVID-19 cases and deaths data, as well as the covariates, on official government sources, such as the Ministry of Health and Ministry of Science and Technology (see Supplementary Appendix Table S2). The intervention information will come from legal documents, official statements, and quantitative accounts from trustable sources.

Covariates

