### *Timing of analyses and outcome assessments*

We will use data from the date of the first case in each country until December 31, 2020. We will use publicly available daily data for all outcomes. We will use the enforcement date on data on interventions collected from PoliMap ([www.polimap.org](http://www.polimap.org)).

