Assumption 2. We will explicitly incorporate co-occurring interventions in a seven-day period as a combination of interventions. We will also adjust for changes in the case definition of COVID-19 cases and deaths for each of the respective outcomes. We will report in the Supplementary Appendix the exact dates considered in the analysis for each country/subnational unit and the interventions included in each intervention period.

Assumption 3. We will introduce flexible spline functions to account for seasonality and long-term trends. We will add a scale parameter, which will be the Pearson statistic divided by the residual degrees of freedom, to account for potential overdispersion (a violation of the Poisson regression assumption). We will test for autocorrelation using the Durbin-Watson tests and visual plots of the autocorrelation function and partial autocorrelation function. If there is evidence of autocorrelation, we will use the Newey-West method to obtain adjusted standard errors.

Therefore, in the final analysis, we will use Poisson regression to model the count data.. The final model is an extension of the regression described in equation 1 with the specifications described above. The model will include each of the interventions (either as single interventions or combinations of), denoted  $j = 1, \dots, J$ . This method allows estimating simultaneously the effect of several interventions. We will consider interventions implemented within a 7-day period as a combination of interventions, following previous studies. This means that the maximum number of combinations of interventions is 52,  $t = 1, \dots, 52$ . We will estimate the effect of the interventions separately when interventions are separated by at least seven consecutive days and for a maximum period of 30 days. The primary analysis will include a 7-day lag to account for the delay in the intervention to be effective, considering the incubation period of SARS-COV2.

$$(5) \ln(Y_t) = \beta_0 + \beta_{1j}time_{tj} + \beta_{2j}post_{tj} + \beta_{3j}timepost_{tj} + \mu_t$$

This model will be run at the municipal level and, therefore, we expect to run 10,000 regressions multiplied by the number of combinations of interventions at each municipal level. Coefficient  $\beta_{3j}$  is the coefficient of interest and represents the change in slope after the intervention  $j$  at period  $t$ .

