In coefficient of interest at a second stage, we will pool the effects for each intervention -or combination of interventions- (i.e. the coefficient of interest  $\beta_{3j}$  from the local level regression) using a random-effects meta-analysis. This meta-analysis will provide information to obtain a pooled effect estimate and a measure of heterogeneity. We will use the  $I^2$  as a measure of heterogeneity.

If the heterogeneity is moderate or high ( $I^2$  higher than 50%), we will carry out a meta-regression to assess whether subnational level determinants can explain the observed heterogeneity. We will analyse the following covariates: (i) Population size, (ii) Population density, (iii) Proportion of population over 60 years old, as a proxy for age structure of the population, (iv) Household density, and (iv) Proportion of population with basic education, as a proxy of socioeconomic status.

The meta-regression has the effect size  $\widehat{\theta}_k$  of a first-stage regression  $k$  as the outcome, covariates  $x_{ik}$ , a fixed effect  $\rho_1 S_a$  for the second-tier level  $a$  (i.e. State or Region) and a random-effect  $\delta_2 N_b$  for the national level  $b$  and a fixed effect  $\rho_2 Y$  for the time of the year (quarterly periods)(equation 6). The equation includes two types of independent errors, where  $\varepsilon_k$  is the sampling error of the effect size and  $\varsigma_k$  is the random-effect error term.

$$(6) \theta_k = \gamma_1 x_{1k} + \dots + \gamma_n x_{nk} + \rho_1 S_a + \delta_2 N_b + \rho_2 Y + \varepsilon_k + \varsigma_k$$

These controls for higher levels of administration and time of the year will allow us to control for constant characteristics at the subnational and national level, as well as changes in the effectiveness throughout the pandemic.

We will carry out the following sensitivity analyses: (1) comparison of effect estimates using a 5-day and 10-day lag; (2) quasi-myopic analyses to control for anticipatory effects (if there is evidence of), and (3) placebo tests evaluating changes at times when no policy was implemented. In the analyses for the number of cases and time-varying R, we will run additional sensitivity analyses estimating the number of SARS-CoV-2 cases corrected by under-ascertainment derived from mortality statistics.

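### One incubation-based lag and a 30-day limit cover all policies, so a null for a policy that works only on delivery (tests, beds, payments) cannot be read as ineffectiveness

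*SAP*

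**What the plan says.** - **Time zero.** SAP, Timing of analyses and outcome assessments: "We will use the enforcement date on data on interventions collected from PoliMap". The term is not defined further.
- **Lag.** SAP, Analysis methods: "The primary analysis will include a 7-day lag to account for the delay in the intervention to be effective, considering the incubation period". The protocol's Outcomes section agrees: "We will consider a 7-day lag as the primary lag".
- **Window.** Effects are estimated separately when interventions are "separated by at least seven consecutive days and for a maximum period of 30 days". The SAP does not say whether the 30 days run from enforcement or from the end of the lag.
- **Alternatives.** The lag sensitivity analysis is a "comparison of effect estimates using a 5-day and 10-day lag".
- **Scope.** Protocol Table 1 has 13 labels: eight on viral spread, two on health systems (testing capacity, and "Interventions to increase the number of ICU/critical beds", both for deaths only) and three on mitigation (direct social assistance, cash transfer, pension withdrawal). No section gives any of them its own clock, lag or window.
- **The plan's own warning.** In its discussion of Assumption 3, the SAP counts ignoring a policy's delayed onset as a misspecification. The remedies listed are splines, a scale parameter and Newey-West errors, plus the 7-day lag. None of these concerns delivery time.

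**The concern.** The lag is chosen "considering the incubation period of SARS-COV2". That suits an order that changes contact on the day it takes effect. It does not describe a bed that has to open, a test that has to reach a laboratory or a payment that has to arrive. For those five labels, enforcement may mark the start of roll-out, with exposure starting later. The days in between are then coded as post-policy, and the 30-day limit may close the window before most of the effect can show.

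Two conclusions are at stake. The protocol pools each intervention or combination to learn whether it worked, so a null for a slow-delivery policy could be taken as lack of effect. Differences in delivery speed between municipalities would also enter the spread of the slopes and hence I², which triggers the meta-regression above 50%. This point is about when exposure starts. It is separate from the delay between infection and death.

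**Working it through.** The plan states no figure on this point, so there is none to reproduce. The calculations below show the size.

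**Inputs from the documents.** Lag 7 days; limit 30 days; alternative lags 5 and 10 days; outcome a 7-day moving average; coefficient of interest the slope change in equation 5.

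**Assumptions not in the documents.** Delay D from enforcement to delivery; true slope change −0.03 per day; baseline slope 0 or 0.03 per day; 60 pre-policy days; one policy, no noise, no spline.

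**Two readings of the limit.** Reading A: 30 days after the lag, days 7 to 36. Reading B: 30 days from enforcement, which leaves 30 − 7 = 23 days, days 7 to 29.

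**Step 1, day counts.** Window days before delivery = D − 7.

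| D | Reading A | Reading B |
|---|---|---|
| 14 | 7/30 = 23% | 7/23 = 30% |
| 21 | 14/30 = 47% | 14/23 = 61% |
| 28 | 21/30 = 70% | 21/23 = 91% |
| 35 | 28/30 = 93% | 100% |

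Most window days precede delivery once D − 7 exceeds 15 (A) or 11.5 (B), that is from D = 23 or D = 19.

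**Step 2, share of the slope change recovered.** Daily mean = exp(a + g·t − 0.03·max(t − D + 1, 0)), with g = 0 or 0.03, smoothed by a trailing 7-day mean. Fit a Poisson regression with intercept, time, post and timepost, the last two starting at day 7. Report fitted β₃ divided by −0.03; each range spans the two values of g.

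| D | Reading A | Reading B |
|---|---|---|
| 7 | 96–97% | 94–95% |
| 14 | 73–77% | 60–64% |
| 21 | 40–46% | 19–23% |
| 28 | 12–15% | 1% |
| 35 | 0–1% | 0% |

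**Step 3, dependence on set-up.** Without the moving average, and with 30 pre-policy days and g = 0.03, the shares are higher: 0.89, 0.60 and 0.27 at D = 14, 21 and 28 under A, and 0.81, 0.39 and 0.04 under B. If the effect needs a further 7 days after delivery, they fall to 0.60, 0.27 and 0.02 (A) and 0.39, 0.04 and 0.00 (B). The decline has the same shape throughout; the exact percentages are illustrative.

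**Step 4, do the planned checks help?** At D = 28, with the window ending one day later than in step 2, the 10-day lag recovers 25–30% (A) or 2% (B), against 14–18% or 1–2% with the 7-day lag. The 5-day lag moves the break further from delivery. The three planned lags could agree with one another while all miss most of the effect.

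**The case against.** Several stronger readings are tempting, and the documents do not support them.

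- **That the plan would rank contact restrictions above capacity and mitigation policies.** No section compares or ranks policy domains. Each intervention or combination is pooled separately.
- **That these policies are biased towards zero and will look ineffective.** This needs the pre-policy log-linear trend to continue. The SAP itself says epidemic curves are non-linear. Fitting equation 5 without a spline to a curve with no policy effect, whose growth rate halves every 30 or 60 days (assumed), gave slope changes of −0.019 to −0.061 per day, so an undelivered policy could look effective. The size depends on the assumed curve; the sign is what matters here. The planned splines may reduce this, and they could also absorb a late effect.
- **That they are scored mainly on days before delivery.** True only from about 19 to 23 days. At two weeks the estimate is attenuated but not null.
- **That five of 13 estimates are affected.** Policies starting within seven days of each other are merged. A cash transfer enacted with a lockdown has no slope of its own.

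The premise also depends on D. Enforcement date is undefined and could mean the day a measure became operational, and the protocol's Data sources section lists quantitative accounts as well as legal texts. Finally, the effect of enacting a policy, slow roll-out included, is a legitimate question, and on that reading differences in delivery speed are genuine heterogeneity.

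All of this stands. It argues against re-dating the primary analysis, as do two further points: local delivery dates may respond to the epidemic, and new dates would change the combinations. It does not answer the narrower point. The SAP gives its lag a purpose, "The primary analysis will include a 7-day lag to account for the delay in the intervention to be effective", and incubation does not measure that delay for these five labels. No planned check reaches three weeks.

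**Conclusion.** The point holds in limited form and is a cheap improvement. For a delivery-dependent policy estimated on its own, or in a combination made up only of such policies, the primary analysis and its lag checks lose much of the effect once delivery takes about three weeks, and nearly all of it by five. Where the 30 days start matters as much as the lag: at D = 21 it moves the recovered share from 40–46% to 19–23%.

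These sizes rest on an assumed D and on a single-policy, noise-free model without splines, in which the pre-policy trend continues. With a bending epidemic curve or overlapping policies the error could go either way. The conclusion that survives is about interpretation: a null for these labels is not evidence of ineffectiveness, and some of their I² may reflect delivery speed.

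**What to change.** Keep the enforcement-date analysis as primary, and change the SAP's Analysis methods section in three places.

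1. In the final-model paragraph, state whether the 30 days run from enforcement or from the end of the lag.
2. In the sensitivity-analysis paragraph, add one analysis for the five labels and for combinations made up only of them. Exclude the days from enforcement to an assumed delivery at 14, 28 and 42 days, then apply the lag and the 30-day window. Where a first delivery date is documented, use it in this analysis.
3. State that a null in the primary analysis for these labels will not be interpreted as ineffectiveness unless it persists across this range.

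The assumed-delay runs need no new data. The cost is a few more model runs and a longer projection of the pre-policy trend: delivery at day 42 plus the lag and window reaches about day 42 + 7 + 30 = 79, with more overlap with other policies. Results at the longer delays should be read with that in mind.

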### *Protocol deviations*

There have not been any deviations from protocol.

### *Study population*

The study will focus on local governments, third-tier administrative units in each country. These receive different denominations in each country, primarily called municipality, district or cantón. The eligibility criteria are (1) Spanish or Portuguese speaking countries in the

Americas; and (2) availability of open data for any of the outcomes of interest at a subnational level. A flow diagram (similar to those recommended by CONSORT guidelines) will be reported describing the number of countries and subnational units eligible and how many of them fulfilled the eligibility criteria.

We will report (as a Supplementary Table) a summary of the baseline characteristics of the local governments included in the study.

#### *Outcome definitions*

The first outcome will be the 7-day moving average of daily confirmed cases of COVID-19/SARS-CoV-2. The second outcome is the time-varying reproductive number between the current and previous period. The third outcome is the 7-day moving average of the daily number of deaths by COVID-19 in Latin American subnational regions. For the statistical modelling, these averages will be rounded to the nearest integer. We will consider a 7-day lag as the primary lag. We will use the definition of COVID-19 case and death which is valid at any given time in each country.

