The first model at the local level does not include covariates (see below). The second model (i.e. the meta-analysis), we will examine the change in heterogeneity after adjusting for several covariates at the local level. Local level covariates include projected population size in 2020, demographic density, age-structure of the population, household density and socioeconomic status. We will use data from official sources of information, primarily the latest national population census in each included country.

Statistical analysis

The Statistical Analysis Plan provides details on the modelling assumptions. We will use an interrupted time series design, where each local government acts as its own control.^{20,21} The main

strength of this design is its capacity to distinguish the effect of the intervention from secular change.²² We will use a Poisson regression to model the count data (for both outcomes) and accounting for overdispersion and secular trends.²³ A full discussion on potential biases and violations of assumptions can be found in the Statistical Analysis Plan.

In a second stage, we will use random effects meta analysis to pool the effect estimates for each intervention or combination of interventions. This analysis informs whether any implemented intervention was effective to reduce COVID-19 cases and deaths and the degree of heterogeneity between the effects at the local level. If we observe high levels of heterogeneity (defined as higher than 50%), we will also use standard meta-regression techniques to assess whether local level determinants (see *Covariates*) can explain the observed heterogeneity.

We will build the models and test the analytical strategy using publicly available data on COVID-19 cases and deaths from Finland and Sweden from January 1 to March 31.

References

2. United Nations Department of Economic and Social Affairs. World Social Report 2020: Inequality in a rapidly changing world. New York, United States: United Nations; 2020.
3. World Health Organization. Report of the WHO-China Joint Mission on Coronavirus Disease 2019 (COVID-19)2020. <https://www.who.int/docs/default-source/coronaviruse/who-china-joint-mission-on-covid-19-final-report.pdf> (accessed March 26, 2020).

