where  $Y_t(1)$  is the sequence of outcomes if we treat the unit at time  $p$  and  $Y_t(0)$  the sequence of outcomes in the absence of treatment. Assumption 1 implies no anticipation of treatment, i.e.  $Y_t(1) = Y_t(0)$  for all  $p \leq t_0$ . In other words,  $\alpha_0 = \theta_0$  and  $\alpha_1 = \theta_1$ . Assumption 2 implies that  $\theta_2$  and  $\theta_3$  are equal to zero.

Violations of assumption 1 include anticipation effects when the subjects of the policy can anticipate its initiation and change their behaviour. In the case of the COVID-19 pandemic, the population might, for example, be more likely to adhere to social distancing recommendations during the discussion of a lockdown or take preventive actions when the incidence of cases increases, even before restrictions such as lockdowns are implemented. Violations of assumption 2 include concurrent changes due to history (other concurrent policy, program or societal changes), selection (changes in the composition of the sample at time  $p$ ), instrumentation (changes in the way the outcome is measured) and mis-specification of the functional form of the time trend (in a classical ITS, time is assumed to be a simple linear term). Violations of assumption 3 can occur due to misspecification of the functional form, including failing to account for a delay of the policy to take effect or failing to account for autocorrelation (which can lead to artificially low standard errors). In an epidemic process, cases over time follow a non-linear trajectory (often an exponential, Gompertz or other complex functional forms). Assuming a linear time trend can lead to incorrect counterfactuals and biased effect estimates.

We will examine and handle potential violations to assumptions in the following way:

Assumption 1. We will assess the existence of anticipation effects by visual exploration and examination of the slope prior to the intervention. If there is evidence of potential anticipation effects, we will use a “quasi-myopic” sensitivity analysis, i.e. an analysis that excludes a period of time where anticipation is expected to have happened from the analyses.

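### Cases and deaths are modelled as overlapping 7-day averages; with an unspecified Newey-West correction and short post-periods, I² can pass the 50% trigger when there is no heterogeneity

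*SAP*

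**What the plan says.** The Protocol (Outcomes) and the SAP (Outcome definitions) both define the case and death outcomes as 7-day moving averages, and both state: "For the statistical modelling, these averages will be rounded to the nearest integer". The reproduction number is not one of these averages and is outside this point.

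SAP, Analysis methods, keeps the day as the unit and fits a Poisson interrupted time series in each municipality. For overdispersion: "We will add a scale parameter, which will be the Pearson statistic divided by the residual degrees of freedom". For serial dependence: "We will test for autocorrelation using the Durbin-Watson tests and visual plots of the autocorrelation function and partial autocorrelation function", and then "If there is evidence of autocorrelation, we will use the Newey-West method to obtain adjusted standard errors". No bandwidth, prewhitening or small-sample rule is given. On duration, effects are estimated separately when "interventions are separated by at least seven consecutive days and for a maximum period of 30 days".

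The slope changes are then pooled by random effects. If I² exceeds 50%, "we will carry out a meta-regression to assess whether subnational level determinants can explain the observed heterogeneity". The Protocol (Statistical analysis) uses the same threshold: "If we observe high levels of heterogeneity (defined as higher than 50" per cent).

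The SAP names the general danger, "failing to account for autocorrelation (which can lead to artificially low standard errors", but neither document notes that the chosen outcome itself creates autocorrelation. Eligibility (SAP, Study population) rests on data availability; there is no rule for series without events.

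**The concern.** A moving average fitted day by day is a set of overlapping observations. It looks smoother than the data behind it, so residual-based standard errors come out too small unless the correction recovers all the hidden variance. Newey-West does so only with a suitable bandwidth and a long series, and this plan guarantees neither.

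I² compares the spread of municipal estimates with their standard errors. If those are too small, sampling error is read as heterogeneity. The second aim is to measure local heterogeneity, and I² decides whether the third aim, explaining it, is pursued. Both could rest on an artefact.

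**Working it through.** The documents give no standard error, expected I², alpha or power, so there is no planned figure to reproduce. Inputs from the documents: 7-day window, daily unit, at most 30 days per effect, 50% trigger. Daily counts, series lengths, Newey-West lags, spline degrees of freedom and the nominal 5% level are assumptions.

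**1. Built-in autocorrelation.** For a 7-day average of independent days the lag-k autocorrelation is (7−k)/7, so 6/7 = 0.86 at lag 1. In a long series Durbin-Watson is then about 2(1−0.86) = 0.29. In simulated short series it averaged 0.56–0.85 and the test fired in 96–100% of series, so the Newey-West branch is nearly always taken.

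**2. Pearson scale.** The average of seven Poisson days has variance λ/7, so the scale is about 1/7 = 0.14 and shrinks the standard error. Because Newey-West usually replaces that standard error, the scale is not the main cause.

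**3. Newey-West in an endless series.** The long-run variance factor is 1 + 2(6+5+4+3+2+1)/7 = 7. Bartlett weights to lag L recover the share [1 + 2Σ(1−k/(L+1))(7−k)/7]/7, summing over k up to L:
- L = 3: (1 + 2×1.143)/7 = 0.469
- L = 4: (1 + 2×1.429)/7 = 0.551
- L = 6: (1 + 2×1.857)/7 = 0.673

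If r is the ratio of reported to true standard error, I² is about 1−r² with no true heterogeneity, and it passes 50% once r < 0.71. Here r² is the share recovered, so I² is about 53%, 45% and 33%. Smoothing alone therefore brings I² near the trigger; short series push it well past.

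**4. Short series, independent days, no true heterogeneity, no spline unless stated.** Set A: 1,000 series per setting, no effect, 10 or 50 cases/day, Poisson or overdispersed. Set B: 2,000–3,000 series, a common slope change, daily means 2–100.

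| Analysis | SE / true SD | Rejection at 5% | I² |
|---|---|---|---|
| A: smoothed, lags 3–6, 30 post-days | 0.43–0.50 (lag 6) | 35–40% | 80–88% |
| A: same, 4-df spline | – | 31–48% | 75–88% |
| A: smoothed, prewhitened, 30 post-days | – | 16–20% | 60–76% |
| A: same, 4-df spline | – | 8–32% | 21–81% |
| A: smoothed, lags 3–6, 155+155 days | – | 15–28% | 47–70% |
| A: smoothed, prewhitened, 155+155 days | – | 2–6% | 0–7% |
| B: smoothed, lags 3–13, 30 post-days | 0.40–0.59 | – | 68–88% |
| B: smoothed, prewhitened, 30 post-days | 0.66–0.98 | – | 36–68% |
| A: raw counts, weekday terms, floored SE, 30 post-days | – | 4–7% | 0–11% |

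Unrounded averages gave 34–41% / 81–87%, so the averaging is the cause, not the rounding. With 60 pre-days and only 7 post-days the ratio fell to 0.15–0.22 (lags 3–13).

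**5. Pooling stage.** 400 null meta-analyses per setting, 200 units each, assumed 5–200 cases/day, lag 6, 30 post-days. I² passed 50% in 100% of them. Rejection was 36–38% for municipal effects, 4–14% for the pooled effect, 5–12% for a null covariate and 3–17% for a size-linked covariate. With raw counts and a floored standard error, I² passed 50% in 0%, and rejection was 4–6% (municipal), 5–7% (pooled) and 3–7% (covariates).

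**6. Autocorrelated transmission.** Assumed AR(1) 0.8, log-SD 0.3, 30% weekday cycle, 30 post-days; rejection / I²:
- smoothed, lags 3–6: 49–55% / 90–93%
- smoothed, prewhitened: 12–20% / 64–76%
- raw counts, floored ordinary Newey-West: 28–44% / 72–86% (82–90% in a separate run)

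Rejection at simulated placebo dates was 30–41%, so a placebo check would expose the problem.

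**7. Series without events.** Rounding turns 0–3 deaths in 7 days into 0 (3/7 = 0.43). Taken literally, an all-zero 30+30-day series enters the pool with slope change 0 and a finite standard error (0.058–0.073 at lags 3–6), although it carries no information. At an assumed 0.10 deaths/day, 88% of rounded 60-day series are all zero, against 0.3% of raw ones.

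**The case against.** The strongest reply is that independent days are an unrealistic null for an epidemic, and that the plan anticipates autocorrelation and names a standard remedy. Step 6 supports part of this. When transmission is itself autocorrelated, raw counts with ordinary Newey-West do worse than the smoothed series with prewhitening. Standard errors of about half size can therefore arise without smoothing, and smoothing with a good correction can avoid them. Short-series Newey-West bias is a separate contributor: applied to independent raw counts at lags 3–7, it gave I² of 37–62%. This stands. The Newey-West specification matters as much as the smoothing, and dropping the average is not a cure by itself.

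It is also fair that the plan states no alpha and no municipality-by-municipality testing, and that first-stage estimates mainly feed the pooling, where the random-effects variance absorbs most of the excess. The municipal rejection rates above therefore measure interval calibration; they do not predict reported findings.

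The reply does not rescue I². In the autocorrelated setting it was above 60% on every path tried with 30 post-days, and with independent days it depends on a choice that the plan leaves open. The trial run on Finnish and Swedish data (Protocol, Statistical analysis) could reveal poor fits, but it has no stated pass criterion.

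**Conclusion.** The point holds for cases and deaths, and it should be fixed. With 30 post-days, independent days and ordinary Newey-West at lags 3–10, municipal standard errors are about 0.4–0.6 of their true size and I² is about 70–90% with no heterogeneity. Prewhitened Newey-West gives ratios of about 0.6–1.0 and I² on either side of 50%. These figures are simulation results under assumed counts and lengths. The 6/7 autocorrelation and the recovery shares in step 3 need only independent days.

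A reader might infer more than this supports:
- *All municipal standard errors are half size.* This depends on lag, prewhitening and length, none of which the documents settle except the 30-day cap.
- *The 50% trigger is always passed.* In one prewhitened setting (mean 20/day, 60+30 days, 300 municipalities) it was passed with probability 0.28.
- *The pooled effects or meta-regression tests are invalid.* Their error rates were near nominal to moderately raised.
- *The pooled death effect is attenuated by a known amount.* That depends on the share of all-zero series, which the documents do not give.

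**What to change.** 1. In Protocol, Outcomes, and SAP, Outcome definitions and Analysis methods, model raw daily counts with day-of-week terms. Keep the 7-day average for plots.
2. Let no standard error, Pearson-scaled or Newey-West, fall below the plain Poisson one.
3. Test autocorrelation on the raw-count residuals, and state the Newey-West bandwidth and prewhitening in advance.
4. Report the rejection rate at the placebo dates already planned in the SAP, against a numeric limit fixed beforehand. If it is exceeded, do not read I² as heterogeneity or use it as the trigger. Items 1 to 3 alone may not restore calibration.
5. Report tau beside I².
6. Secondary: do not pool two-stage estimates from series with no events before or after the change point. Report how many are left out, and note that leaving out series with no post-period events removes the largest declines.

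Cost: wording changes in both Protocol and SAP, because the Protocol defines the outcome, plus code. Daily data are already the source (SAP, Timing of analyses and outcome assessments). Municipal intervals become wider, a few parameters are added, and many small municipalities get no separate death estimate. Placebo dates need policy-free stretches, which may be few in some countries.
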